### 3.5 Primary endpoint(s)

The following primary endpoint(s) will be evaluated, by group:

- Concentrations of IgG antibodies specific to the AlpN proteins in cord blood from each baby:
  - The geometric mean antibody concentrations at birth will be calculated
  - The proportions of babies who achieve a concentration of IgG specific to the AlpN proteins above 0.1, 0.2, 0.5, 1, 2, 4 and 8  $\mu\text{g}/\text{mL}$  at birth will be calculated

The primary immunological endpoint analysis will include the values of these endpoints at the time of delivery, anticipated to be approximately 18 weeks (4  $\frac{1}{2}$  months) from administration of the first dose at 22 weeks GA, or 14 weeks (3 $\frac{1}{2}$  months) from administration of the first dose at 26 weeks GA.

If cord blood cannot be obtained, venous infant blood may be collected within 72 hours of birth.

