### Visit 7, Day 82-86:

The following will be undertaken, and results recorded:

Obstetric examination\* (fundal height, foetal movement and foetal heart rate), height (from screening) and weight (for calculation of BMI), vital signs, safety laboratory tests, immunogenicity maternal blood sample, assessment of the injection sites and review of the eDiary incl. transfer of AEs and CMs to the eCRF (and instruct how to end the eDiary).

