## 7.9 Analysis of immunogenicity (secondary endpoints)

The following secondary immunogenicity endpoints will be evaluated by standard tabulation by vaccination group and relevant time-point(s):

Based on samples collected in the mother (MIG analysis set):

- Concentrations of IgG antibodies specific to the 4 AlpN proteins in maternal blood, pre-dosing, 4 weeks after each vaccination dose and at delivery
- Relative to baseline (pre-dose) concentrations of IgG antibodies specific to the 4 AlpN proteins in maternal blood, pre-dosing, 4 weeks after each vaccination dose and at delivery
- The proportions of mothers who achieve a concentration of IgG specific to the 4 AlpN proteins above 0.1, 0.2, 0.5, 1, 2, 4 and 8 µg/mL at delivery
- The subject level ratios of antibody concentrations between maternal and cord blood at delivery

Based on samples collected in the baby (BIG analysis set):

- Concentrations of IgG antibodies specific to the AlpN proteins in infant blood of each baby at 1 month and 3 months of age:
- The proportions of babies who achieve a concentration of IgG specific to the AlpN proteins above 0.1, 0.2, 0.5, 1, 2, 4 and 8 µg/mL at 1 month and 3 months after birth will be calculated

For treatment groups 1 to 4, in a joint analysis, the maternal IgG concentrations from pre-dosing to delivery will be analysed using a log-normal model with repeated measurements within subject, vaccination group and visit as factors. Possibly allowing for changing variance across visits and visit times group interaction. In this way the ratio of GMCs (GMCR) comparing vaccination groups can be derived.

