For treatment groups 1 to 4, in a joint analysis, the maternal IgG concentrations from pre-dosing to delivery will be analysed using a log-normal model with repeated measurements within subject, vaccination group and visit as factors and a visit \* group interaction.

An unstructured covariance structure will be implemented for repeated measurements. In case of estimation issues, an auto-regressive AR(1) covariance structure will be used instead to model the correlations within-subject. The Satterthwaite approximation will be used to estimate denominator degrees of freedom and adjust standard errors.

Pseudo code related to the implementation of this model:

```
proc mixed data = IgG data;  
  class subject group visit region;  
  model change_log_titre = baseline region group*visit / ddfm=sat;  
  repeated visit / subject=subject type=UN;  
  lsmeans group*visit / diff cl obsmargins;  
run;
```

Here *change\_log\_titre* is the change from baseline in log(titre), *baseline* is the log(titre) at baseline and *visit* is the study Visit (i.e., 3, 5, 7, 8).

Least square mean estimates of change from baseline in log(titre) with 95% confidence intervals (CI) will be presented after applying the inverse transformation at each time-point for each treatment group.

Estimated group differences at Visit 7 and 8 (when vaccination schedule has been completed) between vaccination groups along with associated 95% confidence intervals and p-values will be presented.

Estimated least square means and associated 95% CI of change from baseline in log(titre) will be plotted over time by treatment group.

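### The plain AR(1) fallback in the maternal IgG model forces one variance on all visits, so if it were used the Visit 7 and 8 confidence intervals could be misstated in either direction

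*SAP*

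**What the plan says.** SAP 4.6 describes a joint log-normal model for maternal IgG in Groups 1 to 4. The outcome is change from baseline in log titre, the modelled visits are 3, 5, 7 and 8, and means are fitted for each group at each visit. On covariance it says: "An unstructured covariance structure will be implemented for repeated measurements". If that fit has estimation issues, "an auto-regressive AR(1) covariance structure will be used instead". The pseudo-code uses `type=UN` with Satterthwaite degrees of freedom and no empirical (sandwich) standard errors. No other fallback is named, and the SAP does not say what counts as an estimation issue.

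The results to be presented include: "Estimated group differences at Visit 7 and 8 (when vaccination schedule has been completed) between vaccination groups along with associated 95% confidence intervals", with p-values. Least-squares means with 95% intervals are also shown for every group at every time point.

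Protocol 7.9 describes the same model more loosely: "Possibly allowing for changing variance across visits and visit times group interaction". Neither document gives an SD or a correlation for maternal IgG at any visit.

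**The concern.** Plain AR(1) has two parameters: one variance shared by all visits, and one correlation per visit step. The variance feature is the questionable one. At Visit 3, before the second injection, Groups 1 and 4 (120 of the 240 women in this model) have had saline only, while Groups 2 and 3 have had one active dose. By Visit 7 every regimen is complete. The spread of change from baseline may well differ between those stages, and the fallback removes the visit-specific variances that the unstructured matrix provides and the protocol had in mind.

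A model-based standard error at Visit 7 or 8 would then use a variance averaged over all visits instead of the variance at that visit. Satterthwaite degrees of freedom do not repair this. At stake are the intervals and p-values for the maternal regimen comparisons at Visits 7 and 8.

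**Working it through.** **The plan's own figures.** There is none to reproduce for this model. The only design figure, power above 90% for the cord-blood non-inferiority test at 1 µg/mL, concerns another analysis. It does reproduce: exact enumeration of the Newcombe-Wilson rule with 60 per group, rate 22/23, margin 0.15 and a 90% interval gives 96.7%.

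**Inputs from the documents.**
- Four groups of 60.
- Visit 3 at Day 26-30, Visit 5 at Day 54-58, and "Visit 7, Day 82-86". The midpoints are Days 28, 56 and 84, so these steps are 28 days each.
- Delivery (Visit 8), for which protocol 3.5 says "anticipated to be approximately 18 weeks" after a first dose at 22 weeks: 18 × 7 = Day 126. The last step is 126 − 84 = 42 days, and it varies.

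**Assumptions.** Visit SDs on the log scale, and a true correlation of ρ^(gap/28). Data are complete. The baseline and region covariates are left out.

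**Method.** For a true covariance S, find the AR(1) matrix V with elements σ²r^|i−j| that minimises log|V| + tr(V⁻¹S). With complete data, the group-by-visit means do not depend on V, so at visit t:
- SE ratio = σ / SD_t
- coverage of a nominal 95% interval = 2Φ(1.96 × ratio) − 1

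**Results.** Ranges run over ρ of 0.5, 0.8 and 0.9 for the first three rows and at least 0.5 and 0.8 for the others.

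| SDs at Visits 3/5/7/8 | SE ratio, Visits 7 and 8 | Coverage |
|---|---|---|
| 0.5/1/1/1 | 0.849-0.893 | 90.4-92.0% |
| 0.75/1/1/1 | 0.909-0.938 | 92.5-93.4% |
| 0.9/1/1/1 | 0.961-0.973 | 94.0-94.4% |
| 1/1/1/1 (unequal spacing only) | 1.00 | 95.0% |
| 1.2/1.2/1/1 | 1.105 | 97.0% |
| 1/1/1/1.2, Visit 7 | 1.06-1.08 | about 96% |
| 1/1/1/1.2, Visit 8 | 0.88-0.90 | about 92% |

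Two worked lines: 1.96 × 0.849 = 1.664, and 2Φ(1.664) − 1 = 0.904. Likewise 1.96 × 1.105 = 2.166, and 2Φ(2.166) − 1 = 0.970.

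**Building the SDs from exposure.** Take SD 0.3 with saline only, 1.0 after two doses, and s after one dose. The residual variance at Visit 3 is then the average over two saline-only and two one-dose groups: s = 1.0 gives √((0.09 + 1.00)/2) = 0.74. Comparing AR(1) with the group-pooled Visit 7 variance that the unstructured model would estimate, at ρ = 0.8:

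| One-dose SD s | SE ratio, Visit 7 | Coverage |
|---|---|---|
| 0.8 | 0.87 | 91% |
| 1.0 | 0.92 | 93% |
| 1.2 | 0.96 | 94% |
| 1.5 | 1.02 | 95% |

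**Visit 3 itself.** Its intervals are distorted the other way when its variance is low. At SD 0.75 the AR(1) standard error there is 21 to 25% too large (0.909/0.75 = 1.21; 0.938/0.75 = 1.25).

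**The case against.** The strongest reply is that the planned analysis already handles this. The unstructured matrix gives each visit its own variance, and ten covariance parameters (four variances, six covariances) from about 240 women should be estimable. The protocol wording on changing variance is only permissive, so the fallback does not contradict it. The model is secondary. Protocol 2.5 bases regimen selection on cord-blood IgG and safety, and SAP 4.5 limits even the primary comparisons to descriptive use. All of this stands, and it sets the priority of the point.

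A reader might go further and infer that the fallback makes the Visit 7 and 8 intervals too narrow. The documents do not support a direction. That result follows only if the Visit 3 variance is lower than the later ones. If saline-only SD were 0.3 and one-dose SD 1.4, the pooled Visit 3 SD would be √((0.09 + 1.96)/2) ≈ 1.0, the same as the later value assumed above. If earlier variances are higher, the intervals are too wide. The exposure-based scenarios lean towards too narrow, but they too are assumptions.

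A reader might also blame unequal spacing. Visits 3, 5 and 7 are equally spaced, and only the step to delivery differs. With complete data, spacing alone leaves the standard error of a within-visit group difference unchanged (ratio 1.00 above). It could act only through missing values, and protocol 7.8 expects low attrition.

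**Conclusion.** The point holds in a limited form. Plain AR(1) is the only fallback named. It imposes one variance on visits where equal variance is doubtful, and the model-based intervals would carry any error. Under assumed SDs, coverage at Visits 7 and 8 runs from about 90% (Visit 3 SD half the later value) to 97% (SD 1.2 at the two earlier visits), and the error can differ in sign between Visits 7 and 8.

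Unequal variance is likely from the design but not shown, and no direction can be claimed. The effect arises only if the unstructured fit fails, which is unlikely, and only in a secondary analysis. It is a worthwhile tidying of the SAP and not a threat to the trial's conclusions.

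**What to change.** In SAP 4.6, replace the fallback sentence with a fixed order, moving to the next structure only when the previous one fails: unstructured (`type=UN`), then heterogeneous Toeplitz (`type=TOEPH`), then heterogeneous AR(1) (`type=ARH(1)`). Remove homogeneous AR(1). In the same sentence, say what counts as an estimation issue, so that the switch is not a matter of judgement once results are visible.

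Both heterogeneous structures still tie correlation to visit order. That is acceptable here, because with complete data the variances determine the standard errors of interest.

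The cost is one line of SAP text. With four visits, `TOEPH` has 4 + 3 = 7 parameters and `ARH(1)` has 4 + 1 = 5, against 2 for plain AR(1). That is three to five extra parameters, which is trivial with about 240 women.

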### 4.2 Overall design

The present study is a phase II, multicentre, multinational, parallel group, observer-blind, randomised and placebo-controlled study on the Group B Streptococcus vaccine (GBS-NN/NN2), investigating the immunogenicity and safety of four vaccination regimens in healthy, pregnant women, assessing IgG specific to AlpN proteins in cord blood and maternal blood, and the safety profile in mother and baby up to 6 months post-delivery.

There will be five treatment groups; three groups of 60 subjects to receive two doses of GBS-NN/NN2 and one of placebo (saline), one group of 60 subjects to receive one dose of GBS-NN/NN2 and two of placebo, and one group of 30 subjects to receive three doses of placebo (saline), please see Table 1.

The study is observer-blind. There will be an unblinded vaccine administering team, separate from the team assessing the participants for safety tolerability and collecting the blood samples for assessment of the immune response. The analysis of the immune responses will be undertaken across all groups, see Section 7.8. For further information on blinding procedures, see Section 5.

An early analysis of study data will be performed based on primary and key secondary endpoints available up to 72 hours after delivery (Visit 8) (see Section 7.12 for details).

Each dose of 0.5 mL GBS-NN/NN2 contains 50 µg of GBS-NN and 50 µg of GBS-NN2 and 0.5 mg of aluminium, for all vaccination regimens and groups, and will be given by intramuscular injection.

Group 1 will be 60 pregnant women who will receive one injection of placebo (saline) followed by two injections of the investigational vaccine GBS-NN/NN2.

Group 2 will be 60 pregnant women who will receive two injections of GBS-NN/NN2 followed by one injection of placebo (saline).

Group 3 will be 60 pregnant women who will receive one injection of GBS-NN/NN2 followed by one placebo (saline) and a second injection of GBS-NN/NN2.

Group 4 will be 60 pregnant women who will receive one injection of placebo (saline) followed by one injection of GBS-NN/NN2 and a second injection of placebo (saline).

Group 5 will be 30 pregnant women who will receive three injections of placebo (saline).

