#### 1.1.1 Objectives

##### 1.1.1.1 Primary objective: immunogenicity

The primary objective of this study is to compare the concentrations of IgG specific to the Alp proteins (RibN, Alp1N, Alp2N and AlpCN) in cord blood from babies, born to women who received the GBS-NN/NN2 vaccine or placebo, between four vaccination regimens during pregnancy, between the GBS-NN/NN2 and placebo groups:

- Group 1: GBS2 doses GBS-NN/NN2 at 26 & 30 weeks GA, placebo at week 22
- Group 2: 2 doses GBS-NN/NN2 at 22 & 26 weeks GA, placebo at week 30
- Group 3: 2 doses GBS-NN/NN2 at 22 & 30 weeks GA, placebo at week 26
- Group 4: 1 dose GBS-NN/NN2 at 26 weeks GA, placebo at weeks 22 & 30

Furthermore, a pure placebo group (with half the number of subjects) has been added for general reference:

- Group 5: Placebo at 22, 26 & 30 weeks GA

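### The maternal repeated-measures model in SAP 4.6 uses one baseline slope for all four visits; a visit-specific slope could make the Visit 7 and 8 contrasts more precise at almost no cost

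*SAP*

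**What the plan says.** The model statement in SAP 4.6 is "model change_log_titre = baseline region group*visit / ddfm=sat". The response "is the change from baseline in log(titre"), the covariate is log titre at baseline, and visit "is the study Visit (i.e., 3, 5, 7, 8"). On covariance the SAP says: "An unstructured covariance structure will be implemented for repeated measurements"; AR(1) is the fallback. There is no `baseline*visit` term, and neither document discusses the slope on baseline. The outline in Protocol 7.9 names no baseline covariate at all, so the adjustment is an addition by the SAP.

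The reported results are "Estimated group differences at Visit 7 and 8 (when vaccination schedule has been completed) between vaccination groups", with 95% CIs and p-values.

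On exposure, SAP 1.1.1.1 gives Group 1 two "doses GBS-NN/NN2 at 26 & 30 weeks GA, placebo at week 22", and lists "Group 4: 1 dose GBS-NN/NN2 at 26 weeks GA, placebo at weeks 22 & 30". Protocol 4.2 agrees for Group 1: "Group 1 will be 60 pregnant women who will receive one injection of placebo (saline) followed by two injections of the investigational vaccine". Protocol 4.3.2 takes the Visit 3 immunogenicity sample before that visit's injection. Groups 2 and 3 have had one vaccine dose by then.

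**The concern.** After saline alone, a woman's titre should track her baseline, so the change score has a slope near 0 on baseline. After vaccination, if the response depends less than one-for-one on baseline, the slope of the change score is negative. A single coefficient cannot fit both. Generalised least squares gives most weight to the visit with the least residual variance. That is Visit 3, where half of the women are unvaccinated. The common slope then sits near its Visit 3 value, and part of the baseline variation stays in the Visit 7 and 8 contrasts. An unstructured covariance does not repair this, because the restriction is in the mean model.

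At stake is the width of the intervals for a secondary comparison of regimens, which is also part of the early analysis (SAP 6).

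**Working it through.** **The plan's own figure.** None is given for this model. The only power figure (Protocol 7.13, SAP 2.3.1: above 90% at 1 µg/mL) concerns the cord-blood non-inferiority test. It reproduces. With p = 22/23 = 0.9565 and n = 60, SE = √(2 × 0.9565 × 0.0435 / 60) = 0.0372, and 0.15/0.0372 − 1.645 = 2.39, so power is 99.1%. Exact enumeration of the Newcombe-Wilson rule gives 96.7%.

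**Inputs from the documents.** 60 women in each of Groups 1 to 4; Visits 3, 5, 7 and 8; the dosing schedule. The spread after two doses follows from the phase I table in Protocol 7.13, assuming log-normality:
- Rib-N: 82.61% above 2 and 60.87% above 4 give SD = ln 2 / (0.939 − 0.276) = 1.05.
- AlpC-N: 91.30% and 73.91% give ln 2 / (1.359 − 0.641) = 0.96.

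I use a total ln SD of 1.0.

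**Assumed, because the documents are silent.** ln baseline SD s = 0.8 (also 0.5 and 1.0). Slope of log titre on baseline: 1 after saline, 0.6 after one dose, 0.3 after two. The slope of the change score is therefore 0, −0.4 and −0.7. Saline-phase SD 0.25; residual correlation 0.8.

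**Slope needed at each visit (mean over Groups 1 to 4).**
- Visit 3: (0 − 0.4 − 0.4 + 0)/4 = −0.20
- Visit 5: (−0.4 − 0.7 − 0.4 − 0.4)/4 = −0.475
- Visits 7 and 8: (−0.7 − 0.7 − 0.7 − 0.4)/4 = −0.625

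**Why Visit 3 dominates.** Residual variance after two doses is 1 − 0.3² × 0.64 = 0.942, and after one dose 1 − 0.6² × 0.64 = 0.770. Pooled over groups it is (0.0625 + 0.770)/2 = 0.42 at Visit 3, against (3 × 0.942 + 0.770)/4 = 0.90 at Visits 7 and 8. In simulations of the planned model (240 women, unstructured covariance, feasible GLS, 1,500 trials) the common slope came out at −0.19.

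**Effect on a contrast.** With complete data, and ignoring error in the slope, the Group 2 (or 3) versus Group 1 contrast at Visit 7 or 8 has variance (2/60) × [residual variance + s² × (true slope − fitted slope)²].
- Common slope: 0.942 + 0.64 × (−0.70 + 0.19)² = 1.109
- Visit-specific slope: 0.942 + 0.64 × (−0.70 + 0.625)² = 0.946
- SD ratio: √(1.109/0.946) = 1.08

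The same formula at the other baseline SDs, with simulated common slopes of −0.21 (s = 0.5) and −0.18 (s = 1.0):

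| ln baseline SD | SD ratio, formula | SD ratio, simulated | SD reduction, simulated |
|---|---|---|---|
| 0.5 | √(1.038/0.979) = 1.03 | 1.02–1.03 | 2–3% |
| 0.8 | 1.08 | 1.07–1.09 | 7–8% |
| 1.0 | √(1.180/0.916) = 1.14 | 1.12–1.15 | 11–13% |

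The last column is 1 − 1/ratio. Mean error in the simulated contrasts was about 0.

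**Sensitivity.**
- At s = 0.8 the empirical SD is 5–6% larger under the common slope at residual correlation 0.5, 11–12% larger at 0.9, and about 5% larger with a total SD of 1.3.
- With 10% missing after Visit 3, the model SE is again 6% larger.
- Simulations with other residual assumptions gave SD reductions of 1–3%, 4–7% and 9–10% at s = 0.5, 0.8 and 1.0.
- With slopes of 0.9 after one dose and 0.8 after two, the gain vanishes (visit-specific to common SD ratio 0.99–1.00).
- At s = 1.3 results diverge. One set of runs gave reductions of 4–9%. Another, which held the total post-vaccine SD at 1.0, below the baseline SD, gave ratios of 1.19–1.28 for two-dose slopes of 0.2–0.5, and up to 1.43 at slope 0. I treat that second set as extreme.

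**Group 4 versus Group 1.** Group 4 has had one dose, so its own slope (−0.4) lies nearer the common one. At s = 0.8 the ratio is √[(0.942 + 0.770 + 0.64 × (0.51² + 0.21²)) / (0.942 + 0.770 + 0.64 × (0.075² + 0.225²))] = √(1.907/1.748) = 1.04; simulated 1.05. At s = 0.5 to 0.7 other runs showed no gain (0.99–1.00).

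**Cost when slopes are equal.** With slope 1 throughout, the simulated SE ratio was 0.998–0.999, a loss of 0.1–0.2%.

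**The case against.** The strongest reply is that the size is unknown. Protocol 2.3 says that natural antibodies exist, but no baseline SD and no slope are given. That stands: every percentage above depends on chosen inputs, and the loss is nil if vaccination leaves the slope near 1. A reader might infer that a common slope cannot hold here, or convert the SD loss into a firm number of wasted women. The documents support neither.

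Second, the practical effect is modest. With a residual ln SD of 1, the SE of a log ratio is √(2/60) = 0.183, so a 95% CI around a ratio of 1 runs from 0.70 to 1.43. A 13% cut gives 0.73 to 1.37. SAP 4.6 attaches no margin or decision rule to these contrasts. This also stands.

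Third, the analysis is secondary. Protocol 2.5 bases regimen selection on cord-blood IgG and safety, the primary analysis in SAP 4.5 does not use this model, and SAP 4.6 also tabulates maternal concentrations by group and time point. The model is given as pseudo code. All of this limits severity.

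None of it defends the single slope. No other section supplies the missing term, and the alternative costs almost nothing when it is not needed.

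**Conclusion.** The point holds as an efficiency matter of low severity. It is certain that the model has one baseline slope and that half of the modelled women are unvaccinated at Visit 3. It is conditional, on post-vaccine titre depending less than one-for-one on baseline, that the Visit 7 and 8 contrasts lose precision. For Groups 2 and 3 versus Group 1 the avoidable part of the SD is about 0 to 13% over the main assumptions. That range is illustrative and not a bound. Group 4 versus Group 1 gains less, or nothing when the baseline SD is low.

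A reader might take this as bias or as an invalid model. It is neither: randomisation keeps the contrasts unbiased on average. A chance baseline imbalance is corrected only in part (a residual of −0.70 + 0.19 = −0.51 log units per log unit of imbalance in the central case, against −0.075 with visit-specific slopes), but that is the same loss of precision seen conditionally and should not be counted twice. Nor does the point reach the cord-blood comparisons.

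**What to change.** In the SAP 4.6 pseudo code replace `baseline` by `baseline*visit`, giving `model change_log_titre = baseline*visit region group*visit / ddfm=sat;`. Leave the covariance, the AR(1) fallback and the `lsmeans` statement as planned. A `baseline*group*visit` term would be needed only to describe Visit 3 itself and is not required for the reported contrasts.

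The cost is one edited term and three extra parameters with about 240 women. Make the change before the data are unblinded for the early analysis. If that has already happened, keep the planned model and show the visit-specific version as a labelled sensitivity analysis.
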